8.2 Masking

Not applicable; this is an open-label study.

8.3 Concomitant Medications and Treatments

Documentation of all medications and ocular therapies used by the subject within 30 days of informed consent and during the study will be made in study source documents.

Use of any topical ocular therapies, either prescription or over-the-counter, are prohibited during the course of the study. Contact lens wear during the study is prohibited.

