7.2 Subject Exclusion Criteria

This study will exclude subjects who meet any of the following exclusion criteria (Note: Ocular exclusion criteria are relevant to both eyes, such that meeting a criterion in either eye excludes the subject from the study):

1. Had received Miebo as a prescription or as a study treatment in previous Miebo clinical studies
2. Have any clinically significant ocular surface slit-lamp findings at Visit 1 and/or, in the opinion of the Investigator, have any findings that could interfere with trial parameters, including:
 - a. History of eye trauma
 - b. History of Stevens-Johnson syndrome
 - c. Active blepharitis or lid margin inflammation
 - d. Dry eye disease secondary to scarring, irradiation, alkali burns, cicatricial pemphigoid, or destruction of conjunctival goblet cells (as with vitamin A deficiency)
 - e. Abnormal lid anatomy causing incomplete eyelid closure
 - f. Abnormal cornea shape (keratoconus)
 - g. Corneal epithelial defect or significant confluent staining or filaments
 - h. History of herpetic keratitis
 - i. Pterygium
 - j. Ocular or periocular rosacea
3. Use of any of the following ocular therapies within 60 days prior to Visit 1: Vuity[®], any topical ocular steroid treatments, prescription dry eye therapy including varenicline nasal spray, or topical anti-glaucoma medication

4. Had a LipiFlow® procedure, intense pulse light procedure, or any kind of other procedure affecting meibomian glands within 6 months prior to Visit 1
5. Had received or removed a permanent punctum plug within 3 months (6 months for dissolvable plugs) prior to Visit 1
6. Use of any eye drops (prescription or over-the-counter, such as artificial tears or Lumify®) and/or TrueTear™ device (intranasal tear neurostimulator) within 24 hours prior to Visit 1
7. Have active ocular allergies or ocular allergies that are expected to be active during the trial period
8. Have worn contact lenses within 1 month prior to Visit 1 or planned wear during the study
9. Have undergone intraocular surgery or ocular laser surgery within 3 months prior to Visit 1; have undergone refractive surgery within 2 years prior to Visit 1
10. Have active ocular or systemic infection (bacterial, viral, or fungal), including fever
11. Female subjects who are pregnant, nursing, or planning a pregnancy

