12. Female subjects of childbearing potential who are not using an acceptable means of birth control; acceptable methods of contraception include hormonal (oral, implantable, injectable, or transdermal) contraception; mechanical (spermicide in conjunction with a barrier such as a diaphragm or condom) contraception; intrauterine device; or surgical sterilization of partner. For non-sexually active female subjects, abstinence may be regarded as an adequate method of birth control; however, if the subject becomes sexually active during the trial, she must agree to use adequate birth control as defined above for the remainder of the trial
13. Have an uncontrolled systemic disease that, in the opinion of the Investigator, will interfere with the trial
14. Have a known allergy and/or sensitivity to the study treatment
15. Use of any oral medications known to cause ocular drying (eg, antihistamines, antidepressants, etc.) on a non-stable regimen within 1 month prior to Visit 1 or is expected to be unstable during the trial
16. Have taken isotretinoin (eg, Accutane, Myorisan, Claravis, Amnesteem) within 6 months prior to Visit 1
17. Have corrected VA worse than or equal to +0.7 logarithm of the minimum angle of resolution (logMAR), as assessed with Snellen chart at Visit 1
18. Are currently enrolled in an investigational drug or device study or had used an investigational drug or device within 60 days prior to Visit 1

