12.5.3.3 Prior and Concomitant Medications

Concomitant medication use will be summarized using the number and percentage of subjects using each type of medication by drug class and preferred term. Ocular and non-ocular medications will be presented in separate tables. Prior medications will be included in a listing but not included in the concomitant medication summary.

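### Does a 30-day medication look-back leave the 60-day and 6-month washouts without support?

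*Combined protocol and SAP*

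**What the plan says.** Section 8.3 sets the general rule for the medication record: "Documentation of all medications and ocular therapies used by the subject within 30 days of informed consent and during the study" goes into source. Under Section 7.3.1 a subject is enrolled on signing consent at Visit 1, so this means 30 days before Visit 1.

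Section 7.2 uses longer windows for several exclusions:

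- Exclusion 3: "Use of any of the following ocular therapies within 60 days prior to Visit 1", covering Vuity, topical steroids, prescription dry eye therapy and anti-glaucoma medication.
- Exclusion 4: LipiFlow, intense pulse light or "any kind of other procedure affecting meibomian glands within 6 months prior to Visit 1".
- Exclusion 5: "Had received or removed a permanent punctum plug within 3 months (6 months for dissolvable plugs) prior to Visit 1".
- Exclusion 16: "Have taken isotretinoin (eg, Accutane, Myorisan, Claravis, Amnesteem) within 6 months prior to Visit 1".
- Exclusion 18: current enrollment in an investigational study, or the subject "had used an investigational drug or device within 60 days prior to Visit 1".

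Exclusion 15 is close to the Section 8.3 window, since it concerns drying oral medications "on a non-stable regimen within 1 month prior to Visit 1".

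On the analysis side, Section 12.5.3.3 says "Prior medications will be included in a listing" and keeps them out of the concomitant medication summary.

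**The concern.** Read alone, Section 8.3 lets a site stop its medication history at day 30. The log and the prior-medication listing would then hold no entry for days 31 to 60, or for isotretinoin from day 31 to 6 months. A monitor could not confirm those washouts from the log.

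The design makes this worth asking. The study has one open-label arm, and Section 12.2 tests the Day 7 change in symptom severity against zero. If a subject came in while symptoms were still shifting after a stopped therapy, no control arm would absorb that shift. If the breach was also invisible in the data, the subject could stay in the Per Protocol Set as well as the Full Analysis Set.

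**Working it through.** **Size of the mismatch.** The uncovered part of each window is W − 30 days, and its share is (W − 30)/W. Six months is taken as 180 to 183 days and three months as 90 to 91.

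| Section 7.2 criterion | Window W | Outside 30 days | Share |
|---|---|---|---|
| 3 (listed ocular therapies) | 60 days | 60 − 30 = 30 | 50% |
| 18 (investigational products) | 60 days | 30 | 50% |
| 16 (isotretinoin) | 6 months | 150 to 153 | 83 to 84% |
| 4 (gland procedures) | 6 months | 150 to 153 | 83 to 84% |
| 5 (permanent plugs) | 3 months | 60 to 61 | 67% |
| 5 (dissolvable plugs) | 6 months | 150 to 153 | 83 to 84% |
| 15 (drying oral medications) | 1 month | about 0 | about 0% |

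The arithmetic of the concern is right. These are shares of calendar time, however, not of subjects and not of an effect.

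**What else the plan requires for the uncovered days.**

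1. Section 7 makes a subject eligible only if no exclusion applies. The site must therefore establish 60-day and 6-month use for each subject, whatever Section 8.3 says about the log.
2. Section 10.1.1 and the Appendix A flow chart list the inclusion/exclusion check as its own Visit 1 item. Medical/surgical history and previous/concomitant medication are also listed, with no look-back stated there.
3. Section 13.2 requires medical information obtained at a visit to be recorded in the subject's record. The answer to an exclusion question is such information.
4. Section 13.3 requires CRF information to be traceable to source and has the monitor verify it.
5. Section 8.4 requires deviations to be documented, and Section 12.6.3.2 has important ones identified before database lock.

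Two other exclusions show that the log was never meant to evidence every window. Exclusion 1 bars any previous Miebo use with no time limit, and exclusion 9 goes back 2 years for refractive surgery. No 30-day or 60-day log could support either. They rest on history and the eligibility check, and so can exclusions 3, 16 and 18.

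**Link to the results.** The plan gives no figure on this point. Its sample size does not use medication history and reproduces as stated: for n = 75, difference 8.194 and SD of differences 25, paired-t power is 0.79997, and 75/(1 − 0.25) = 100.

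For scale only, suppose one wrongly admitted subject among 75 had a change shifted by a full SD of 25 points. The mean would move by 25/75 = 0.33 points, or 0.33/8.194 = about 4% of the difference the study is powered to detect. The shift of 25 is an assumption. The documents give neither the number of such subjects nor the size or direction of any shift.

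**The case for a change.** The best case for a change is that Section 13.2 covers only information that was obtained. It does not make the site ask for drug names and stop dates beyond 30 days. An exclusion can be marked as not met with no medication entry behind it, and a site that follows Section 8.3 to the letter has done nothing wrong. The protocol rules out waivers, so its criteria are meant to be strict and ought to be checkable. Extending the look-back for a few named therapies would cost one sentence and a little recall effort at Visit 1.

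Part of this stands. The medication log and the listing cannot by themselves corroborate these washouts, and no visible text says what evidence should. It does not follow that nothing is recorded, that source verification must fail, or that breaches stay hidden. Use in the last 30 days must be logged in any case. For earlier use, a subject gets in wrongly only if the eligibility question is missed or answered wrongly. A longer log filled in at the same visit, from the same subject's memory, would often carry the same error. Independent detection would need pharmacy or medical records, which a longer look-back does not bring. The eligibility and medication CRFs and the monitoring plan are not among the documents, so the evidence asked for in practice may already be fuller.

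**Conclusion.** The Section 8.3 look-back is shorter than the windows in exclusions 3 and 18 by 30 days, and shorter than the window in exclusion 16 by about 150 days. This is a minor gap in corroboration that the separate eligibility check fills in ordinary site practice. The two sections do different jobs, one governing the medication record and the other entry, and they do not contradict each other. A longer log would tidy the audit trail, with no demonstrated change to who is enrolled, to the Day 7 estimate or to its test.

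This rests on two assumptions: that sites put the full exclusion windows to subjects at Visit 1, as Section 7 requires, and that the answers are kept in source, as Sections 13.2 and 13.3 require. The documents do not allow an estimate of how often a washout would be breached. No change to the plan is needed.

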8.4 Protocol Deviations

A deviation from the protocol is an unintended and/or unanticipated departure from the procedures and/or processes approved by the Sponsor and the IRB and agreed to by the Investigator.

The Investigator or designee must document and explain in the subjects' source documentation any deviation from the approved protocol. Protocol waivers will not be allowed under any circumstances. The Investigator may implement a deviation from, or a change of, the protocol to eliminate an immediate hazard to study subjects without prior IRB approval. As soon as possible after such an occurrence, the implemented deviation or change, the reasons for it, and any proposed protocol amendment(s) should be submitted to the IRB for review and approval, to the Sponsor for agreement, and to the regulatory authorities, if required.

Deviation impact on data analysis is described in [Section 12.6.3.2](#). The date of and reason for deviations in all cases will be documented. Protocol deviations affecting the safety of the subject or the integrity of the study must be reported promptly by the Investigator to the IRB. Reporting of all other protocol deviations must adhere to the requirements of the governing IRB.

Protocol assessments will continue for a subject until the end of the study, unless the protocol deviation puts the subject at risk or the subject's condition requires that he/she be discontinued from the study.

Scheduled assessments missed or conducted out of window due to Coronavirus Disease 2019 (COVID-19) disruption will be recorded as protocol deviations.

9 Study Materials and Management

9.1 Description of Study Treatment and Intended Use

Miebo (100% perfluorohexyloctane ophthalmic solution) is a semifluorinated alkane indicated for the treatment of the signs and symptoms of DED. Each multiple-dose bottle contains 3 mL of 100% perfluorohexyloctane, 1.338 g/mL, as a clear and colorless liquid.

Miebo is manufactured for Bausch & Lomb Incorporated.

9.2 Packaging and Labeling

9.2.1 Packaging

To maintain product integrity and sterility, Miebo will be supplied in its original primary packaging container (bottle) as part of a kit (2 bottles per kit) and labeled per [Section 9.2.2](#).

9.2.2 Labeling

Study treatment labeling will include the following information:

- Protocol number
- Kit number
- Caution statement
- Storage conditions
- Name and address of the Sponsor

9.3 Storage of Study Treatment

Study treatment will be stored at 15°C to 25°C (59–77°F).

9.4 Directions for Use and Administration

Miebo will be used according to the Miebo prescribing information ([Appendix E](#)).

9.5 Study Treatment Accountability

A dedicated team member at each site will be responsible for keeping current and accurate records of the study treatment received and dispensed and its disposition. Study treatment must be stored under the appropriate conditions in a secure area and is to be used only by subjects enrolled in the study, in accordance with the conditions specified in this protocol. During the course of the study, the dedicated team member must maintain an inventory of all study treatment, including subject identifiers.

Accountability records will include:

- The batch and kit numbers of the study treatment received, the receipt date, and the quantity received
- The names of all site personnel who received or disposed of the study treatment
- The dates of use, disposal, or return of the study treatment
- A record of each subject treated with the study treatment
- Why and how many bottles of study treatment are returned to the Sponsor
- An explanation for reconciliation of discrepancies

At various time points throughout the study and/or upon completion of the study, the Sponsor or Sponsor's representative will review and verify the dedicated team member's accountability records. Following verification, and as directed by the Sponsor, unused study treatment must be returned to the Sponsor.

9.6 Other Materials

Study materials provided by the Sponsor or Sponsor designee will include:

- Ocular Surface Disease Index questionnaire
- Early Outcomes Survey
- Dosing diaries

10 Study Procedures and Evaluations

Subjects will be examined and evaluated according to the study flow chart provided in [Appendix A](#).

10.1 Schedule of Evaluations and Procedures

Enrolled subjects who meet eligibility criteria will be seen in the clinic according to the following schedule (Table 1):

Table 1. In-Clinic Visit Details

Visit Name	Visit Time and Window
Visit 1 (Screening/Baseline Visit)	Day 1
Visit 2	Day 3 ± 1
Visit 3	Day 7 ± 1
Visit 4	Day 14 ± 2

Refer to [Appendix A](#) for the study flow chart and [Appendix B](#) for methods of clinical evaluations.

10.1.1 Screening/Baseline Visit (Visit 1): Day 1

The following study measurements will be collected:

- Informed consent/Health Insurance Portability and Accountability Act

- Demographics
- Medical/Surgical history
- Urine pregnancy test (for female subjects of childbearing potential)
- Previous/Concomitant medication
- [REDACTED]
- [REDACTED]
- Visual acuity
- Tear film break-up time
- Total CFS score
- Meibomian gland dysfunction (MGD score)
- Schirmer's test
- Inclusion/Exclusion criteria

Following subject's confirmation of eligibility, the following will take place starting from at least 15 minutes after the completion of Schirmer's test:

- Instillation of study treatment (instilled bilaterally by site staff)
- [REDACTED]
- Dispensation of study treatment
- Dispensation of dosing diary
- Adverse event query

10.1.2 Visit 2: Day 3 + 1 day

The following study measurements will be collected:

- Concomitant medication
- Adverse event query
- Early Outcomes Survey – Follow-up Visit
- Dosing diary review by dedicated team member

10.1.3 Visit 3: Day 7 ± 1 day

The following study measurements will be collected:

- Concomitant medication
- Adverse event query

- [REDACTED]
- Dosing diary review by dedicated team member

10.1.4 Visit 4: Day 14 ± 2 days

The following study measurements will be collected:

- Concomitant medication
- Adverse event query
- [REDACTED]
- [REDACTED]
- Visual acuity
- Dosing diary review by dedicated team member
- Collection of study treatment and dosing diary
- Trial exit

10.1.5 Unscheduled Visit(s)

Additional visits may be scheduled, as necessary, to ensure the safety and well-being of subjects. All additional examinations should be fully documented in the source documents and on Unscheduled Visit CRFs, as appropriate. Visits intended to fulfill scheduled visit requirements that fall outside the designated scheduled visit window will be collected and transcribed to the appropriate visit CRF.

If a subject is seen for multiple visits during a given visit timeframe, the data from the visit that are intended to meet the protocol requirements for the scheduled visit will be captured on the visit CRF. Where such a determination cannot be made, the first visit within the scheduled visit interval will be used for completion of the protocol-required scheduled visit CRF. Data from any additional visits within a scheduled visit interval will be captured on an Unscheduled Visit CRF.

10.1.6 Missed Visits

If a subject misses any scheduled follow-up visit and cannot be seen prior to the start of the visit range for the next scheduled follow-up visit, the visit is considered missed.

10.1.7 Post-Study Follow-Up

If a subject requires further follow-up upon discontinuation or completion of the study, the Investigator should schedule post-study follow-up visits, as necessary. Refer to [Section 11.3.5](#) for follow-up of AEs following study exit.

10.2 Study Completion

The Sponsor or its representative will notify the Investigator or the IRB, as applicable, to inform them when the study is complete (last subject last visit).

10.2.1 Early Study Termination

If during the study it becomes evident to the Sponsor that the study should be stopped prematurely, the study will be terminated and appropriate notification will be given to the Investigators, IRB, and FDA or Local Health Authority, as applicable. The Sponsor or its representative will instruct the Investigators to stop enrolling and dispensing study materials/treatment and to arrange for study closeout at each site as appropriate.

11 Primary and Secondary Safety and Efficacy Variables

11.1 Evaluation of Efficacy

Efficacy will be evaluated using the following assessments:

- [REDACTED]
- [REDACTED]

11.2 Evaluation of Safety

Safety will be evaluated using the following assessments:

- Adverse events
- Visual acuity

11.3 Adverse Events

Both eyes must be examined for the presence/absence of AEs at all visits, whether scheduled or not. If an AE occurs, the first concern will be the safety and welfare of the subject; treatment should be provided as appropriate for the event.

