5.2.2 Safety

The safety outcomes are as follows:

- Adverse events (AEs; reported, elicited, and observed)
- Visual acuity

6 Investigational Plan

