11.3.1 Adverse Events Definitions

For the purposes of this study, AEs include all ocular AEs/SAEs, and all non-ocular SAEs. Adverse events and SAEs are defined as follows.

An AE is any untoward medical occurrence, unintended disease or injury, or untoward clinical sign (including abnormal laboratory finding) in a subject, user, or other persons, whether or not related to the study treatment. For users or other persons, this definition is restricted to events related to the study treatment.

An SAE is an AE that leads to one or more of the following:

- Death
- A life-threatening illness or injury
- A permanent or significant disability/impairment of a body structure or body function (eg, blindness)
- In-patient or prolonged hospitalization
- Medical or surgical intervention to prevent life- or vision-threatening illness or injury or permanent impairment to a body structure or a body function

- Fetal distress, fetal death, or a congenital abnormality or birth defect

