11.3.2 Identification and Collection

Identification and collection of an AE begins after informed consent has been obtained and documented. Standard sources of identifying AEs include:

- Direct observation by the Investigator
- Asking the study participant a non-specific question (eg, “Have you had any problems since the last visit?”)
- Unsolicited volunteering of information by the study participant (eg, “Doctor, I have had blurred vision since I started using this lens.”)
- Test results that meet protocol requirements for classification as an AE

Specific to this protocol, ocular AEs and all SAEs (ocular and non-ocular) observed or elicited by the Investigator, reported by the subject, or resulting from a test result, etc., occurring during the clinical study must be reported on the CRF. During the study, the Investigator should treat the study subject as appropriate to ensure his/her safety and welfare. Refer to [Section 11.3.5](#) for additional information pertaining to ongoing AEs at subject exit.

Pre-existing conditions will not be considered AEs but will be collected at the Screening/Baseline Visit as medical history. A worsening of a pre-existing condition during the study should be documented as an AE and evaluated accordingly.

Hospitalizations for admission without a medical AE should be captured as an SAE until the cause of hospitalization can be identified. However, the following reports of hospitalization without a medical AE should not be considered either serious or an AE:

- Admission for treatment of a pre-existing condition not associated with the development of a new AE or with worsening of the pre-existing condition (eg, for work-up of persistent pretreatment lab abnormality)
- Social admission (eg, subject has no place to sleep)
- Administrative admission (eg, for yearly physical exam)
- Optional admission not associated with a precipitating medical AE (eg, for elective cosmetic surgery)

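### Will ocular signs go unrecorded because the Visit 2 list does not show the eye examination that Section 11.3 requires?

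*Combined protocol and SAP*

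**What the plan says.** Section 11.3 opens the adverse event (AE) rules with "Both eyes must be examined for the presence/absence of AEs at all visits, whether scheduled or not". Section 10 tells sites: "Subjects will be examined and evaluated according to the study flow chart provided in" Appendix A. The Visit 2 list (Section 10.1.2) has four items: medication review, "Adverse event query", the Early Outcomes Survey and a check of the dosing diary. Section 11.2 begins "Safety will be evaluated using the following assessments" and names AEs and visual acuity. In the flow chart, acuity is marked at Visits 1 and 4 only.

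Observed events count. Section 5.2.2 includes them in the safety outcome alongside reported and elicited ones. Section 11.3.1 includes an "untoward clinical sign (including abnormal laboratory finding) in a subject". Section 11.3.2 gives "Direct observation by the Investigator" as a source separate from questioning the participant, and adds: "A worsening of a pre-existing condition during the study should be documented as an AE". Section 12.5.3.1 summarises TEAEs for the Full Analysis Set by counts and percentages.

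**The concern.** A coordinator who runs Visit 2 from Section 10.1.2 could finish every listed item without anyone looking at the eyes. Because Section 11.3.2 treats asking and observing as different sources, the AE query does not plainly include an examination. With up to 8 sites, some might examine and others only ask. A sign without symptoms would then be recorded at some sites and not at others, and the TEAE table would not show which had happened. This would matter because Section 11.3.1 restricts non-serious AEs to ocular ones, so eye findings are the core of the safety data.

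**Working it through.** The point turns on wording, and the plan states no figure to reproduce. The check sets the passages side by side.

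1. **What is legible at each follow-up visit.** Visit 2 (10.1.2): 4 items, none redacted, no eye examination. Visit 3 (10.1.3): 3 legible items, 1 redacted. Visit 4 (10.1.4): 6 legible items including acuity, 2 redacted. Absence from the list can be shown at Visit 2 only.

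2. **Whether the flow chart settles it.** The visible rows marked at Visit 2 are medication, the AE query and diary review. The visible chart is incomplete, however: Section 10.1.2 lists the follow-up survey at Visit 2, yet no row for it survives, and footnote [5] stands without its row. Silence in the visible chart therefore proves little. Appendix B, which holds the evaluation methods, is also unreadable.

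3. **Whether the two instructions conflict.** Section 10.1.2 introduces its items as measurements to be collected and does not say that nothing else is done. Section 11.3 uses mandatory wording and extends to unscheduled visits, for which Section 10.1.5 gives no procedure list at all. It is therefore a standing instruction that does not work through the lists. A site can comply with both sections, and full compliance includes the examination.

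4. **How Visit 1 is handled.** Section 7 requires an ophthalmic examination on Day 1, and that requirement also sits outside the visit list. If text elsewhere in the protocol suffices for Visit 1, Section 11.3 suffices for Visit 2.

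5. **What happens if a site omits it.** Omission would be a departure from Section 11.3, to be documented under Section 8.4. Section 13.1 provides for review of the protocol and CRF with site staff before the start, and for monitoring of protocol compliance. Section 13.2 requires medical information obtained at each visit to be recorded in source. These controls do not guarantee uniform practice, but they address this kind of lapse.

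6. **Size.** At Visit 2, about 100 treated subjects × 2 eyes = 200 eye examinations are called for without a listed slot. That counts required examinations, not missed events. Turning it into an under-count needs a rate of symptom-free signs and a rate of omission, and the documents give neither.

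**The case for a change.** The strongest case for acting is that staff work from visit lists and that a requirement without a slot or a visible recording step is easily overlooked. The remedy looks cheap: a line in the schedule and a CRF field, at visits already held in the clinic. The wording of Section 11.3 may also have been carried over from another study: an example in Section 11.3.2 speaks of a lens, although no lens is studied here and Section 8.3 prohibits contact lens wear. If so, the sponsor may not have intended an examination at every visit.

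Part of this stands. The examination is not visibly scheduled at Visit 2, its content is not defined in any readable passage, and only the sponsor can say whether it is meant at every visit.

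The rest does not carry. Uneven ascertainment assumes that sites will disregard a mandatory sentence. Whether the CRF already has a field for this, or Appendix B a method, cannot be known from what is legible. Baseline corneal staining does not strengthen the case: Section 11.3 does not say that the examination includes staining, break-up time or gland grading, so listing it would not by itself detect worsening of those scores. The reactions named in Section 6.1 of the prescribing information (Appendix E) are blurred vision, which a question can elicit, and conjunctival redness, which can be visible without a scheduled procedure.

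**Conclusion.** No change to the plan follows. Section 11.3 and Section 10.1.2 are compatible. A sponsor following the protocol exactly would examine both eyes at Visit 2, and the descriptive TEAE table would be sound. The fault is a missing cross-reference, demonstrable in one of three follow-up lists. The sponsor can reconcile the sections editorially by stating how Section 11.3 applies at Visit 2; this review takes no view on which clinical procedure is right.

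No under-count is demonstrated and none can be calculated. There is no between-group comparison to bias, and the primary analysis does not use these data. The conclusion assumes that sites treat Section 11.3 as binding and that the redacted material does not contradict it. It would need another look if the sponsor stated that no follow-up examination was intended, because the report would then have to describe how AEs were actually ascertained.
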